## 11.0 STATISTICAL AND ETHICAL CONSIDERATIONS

### 11.1 Sample Size and Study Duration

#### Strata:

Part A: Patients with relapsed or refractory solid tumors (Phase 1)

Part B: Patients with relapsed or refractory HGG (excluding DIPG) who do not require resection

Part C: Patients with relapsed or refractory HGG for whom resection is required

For Part A, a minimum of 2 evaluable patients with relapsed or refractory solid tumors including CNS tumors will be entered at each dose level for determination of MTD. Once the MTD or recommended Phase 2 dose has been defined, up to 6 additional patients with relapsed/refractory solid tumors without restrictions on heme evaluability may be enrolled

THIS PROTOCOL IS FOR RESEARCH PURPOSES ONLY, SEE PAGE 1 FOR USAGE POLICY

to acquire PK data in a representative number of young patients (i.e. patients < 12 years old). A maximum of 29 patients is anticipated in this Part, assuming 6 evaluable patients are required for each dose level, 6 additional patients are needed for PK analysis, and a 20% inevaluable rate. Review of the enrollment rate into previous COG new agent studies indicates that 1-2 patients per month are available, which will permit completion of the study within 15-29 months. In the unlikely event that all dose levels require expansion to 12 patients per [Section 11.2.2](#), then a maximum of 51 patients would be required allowing for a 20% inevaluable rate. This would require about 26-51 months for study completion.

With Amendment #1, an additional 29 patients is anticipated for Part A, assuming 6 evaluable patients are required for each dose level, 6 additional patients are needed for PK analysis, and a 20% inevaluable rate. The maximum accrual for the study (accounting for all parts of the study) will increase from 75 to 81 patients, assuming 20% inevaluability.

Amendment #4 will require a minimum of 4 evaluable patients. The maximum is expected to be 30 allowing for 6 patients at each of three dose levels, 6 for PK, and 20% inevaluability. This is expected to be completed within 15-30 months.

However, a dose level will be repeated with required maximal antiemetic therapy (5-HT3 antagonists and another antiemetic) prior to each dose during Cycles 1 and 2 if DLTs of vomiting or dehydration is experienced in  $\geq 2/6$  evaluable patients at a dose level. This condition would increase the expected maximum to 38 which allows for 12 patients at one dose level, 6 at the two other dose levels, 6 PK, and 20% inevaluability. This would be expected to be completed within 19-38 months.

In the unlikely event that all dose levels required expansion to 12 patients per [Section 11.2.2](#), then the absolute maximum would be 68 patients. This includes 24 patients at a single dose level requiring expansion due to both 1) toxicities of different classes and 2) DLTs of vomiting or dehydration as well as 12 patients at each of the other two dose levels, 6 PK, and 20% inevaluability. This would be expected to be completed within 34-68 months.

The study has currently enrolled 31 patients (Fall 2019 SPR).

Non-Surgical Cohort (Part B): 10 evaluable patients with recurrent/progressive HGG (excluding DIPG) who do not require resection will be enrolled in a medical dose-expansion cohort (Part B) and will be treated at the MTD on the same schedule. If at any time greater than one out of three patients (or 33%) of the cohort of patients experience DLT, the cohort will be closed to further accrual. All patients enrolled on Part A who meet the eligibility criteria for Part B of the study who are evaluable for response as outlined in [Section 11.2.3](#) of this protocol will be included in the evaluation rule.

Surgical Cohort (Part C): Up to 10 evaluable patients with recurrent/progressive HGG (excluding DIPG and disseminated tumors) for whom resection is recommended by their treating teams will be enrolled in a surgical dose-expansion cohort. These patients will be allowed to receive up to four doses of selinexor prior to resection. After their resection and when medically cleared, they will restart selinexor on the prior schedule. The purpose of this cohort will be to perform pharmacokinetic and pharmacodynamic studies on the tumor tissue, and to explore preliminarily the effectiveness of selinexor in this disease. If at any time greater than one out of three patients (or 33%) of the cohort of patients experience DLT, the cohort will be closed to further accrual.

Accrual to Parts B and C will only open once the MTD or recommended phase 2 dose has been determined in Part A, and may open concurrently with the PK expansion described above.

A maximum of 24 patients are expected to enroll in Parts B and C combined, assuming an inevaluability rate of 20%. We anticipate that each part of the study will require 6-12 months for enrollment.

Response for Part B will be defined as either MR, PR or CR on two consecutive 2D measurements on standard imaging done 4 weeks apart (See [Section 12.6](#)). Sustained responses are very rare in this cohort of recurrent non-DIPG HGGs. We will consider the agent of sufficient interest for further evaluation in this disease category if at least one PR or CR, or at least two MRs, is observed among 10 enrolled patients. A response rate of 20% or more would be evidence of sufficient activity. If the true response rate is 20%, then the probability of observing one or more responses among 10 evaluable patients is about 89.3%. If the response rate is 5%, then the probability of observing at least one response is about 40.1%.

Clinical benefit for Part C will be evaluated separately using the criteria of no visible disease progression six months from the start of treatment. If two or more of a cohort of up to six patients are unable to resume therapy within 6 weeks after surgery, the surgical arm will be declared not feasible. If Part B has fully accrued, Part C will close to further accrual.

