## 5.3 Dose Escalation Schema

### 5.3.1 Inter-Patient Escalation: Part A

The starting dose will be 35 mg/m^2 (dose level 1), with dose levels for subsequent groups of patients as follows.

(Pre-Amendment #4): Twice weekly dosing

THIS PROTOCOL IS FOR RESEARCH PURPOSES ONLY, SEE PAGE 1 FOR USAGE POLICY

Table for Dose Levels 1-3.

Dose Level**	Selinexor Dose (mg/m  )
-1	20
1*	35
2	45
3	60 ^

\* Starting Dose Level

^ Further dose escalation will be considered after evaluation of the pharmacokinetics and toxicity profile**Amendment #4:** Once weekly dosing

Table for Dose Levels 1 & 2:

Dose Level**	Selinexor Dose (mg/m  )
-1	35
1*	45
2	55

\* Starting Dose Level

**Amendment #4:** With amendment #4, the starting dose will be 45 mg/m^2. Prophylactic treatment of nausea and emesis (such as 5-HT3 antagonists +/- another agent [e.g., dexamethasone, NK1 receptor antagonist, etc]) is strongly recommended during Cycles 1 and 2 (see [Section 7.3](#)). In adult patients, double antiemetic coverage (5HT3 antagonist + another agent) is preferred. If DLT of vomiting or dehydration is experienced in  $\geq 2/6$  evaluable patients at a dose level outlined in the dose level tables above, the dose level will be repeated with required maximal antiemetic therapy (5-HT3 antagonist PLUS antiemetic agent(s)) prior to each dose during Cycles 1 and 2. Once the requirement for prophylaxis during Cycles 1 and 2 has been made, this will be carried forward for all subsequent patients entered at the same or higher dose level. Dose levels which require antiemetic prophylaxis will be denoted with the suffix letter "A" (e.g. Dose Levels -1A, 1A, or 2A).

Selinexor is supplied by Karyopharm Therapeutics. **Do not use commercial supply.**

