4	≥ 2	0, 1 or 2	0, 1 or 2	De-escalate*
5	0	0, 1, 2, 3 or 4	1, 2, 3, 4 or 5	Same dose level
5	1	0, 1, 2, 3 or 4	0, 1, 2, 3 or 4	Same dose level
5	0	5	0	Escalate**
5	≥ 2	0, 1, 2 or 3	0, 1, 2 or 3	De-escalate*
6	0	0, 1, 2, 3, or 4	2, 3, 4, 5 or 6	Suspend
6	1	0, 1, 2, 3 or 4	0, 1, 2, 3 or 4	Suspend
6	0 or 1	5 or 6	0 or 1	Escalate**
6	≥ 2	0, 1, 2, 3 or 4	0, 1, 2, 3 or 4	De-escalate*

\* If six patients already entered at next lower dose level, the MTD has been defined.

\*\* If final dose level has been reached, the recommended dose has been reached.

If two or more of a cohort of up to six patients experience DLT at a given dose level, then the MTD has been exceeded and dose escalation will be stopped (see [Section 11.2.2](#) for exception to rule).

In addition to determination of the MTD, a descriptive summary of all toxicities will be reported.

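### Section 11.1 calls 68 the absolute maximum for Part A, but counts the antiemetic repeat at one dose level only; section 5.3.1 allows repeats at two or three levels, giving 83 or 98

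*Combined protocol and SAP*

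**What the plan says.** Section 11.1 builds the Part A maximum for Amendment #4 in three steps:

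- A base of 30, "allowing for 6 patients at each of three dose levels, 6 for PK, and 20% inevaluability".
- An expected maximum of 38 if a level has to be repeated with required antiemetics, "which allows for 12 patients at one dose level, 6 at the two other dose levels", plus 6 PK patients and 20% inevaluability. The stated duration is 19-38 months.
- The extreme case: "then the absolute maximum would be 68 patients. This includes 24 patients at a single dose level requiring expansion due to both" causes, "as well as 12 patients at each of the other two dose levels, 6 PK, and 20% inevaluability". The stated duration is 34-68 months.

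The repeat itself is defined in section 5.3.1. It is triggered when DLTs of vomiting or dehydration occur in at least 2 of 6 "evaluable patients at a dose level outlined in the dose level tables above, the dose level will be repeated with required maximal antiemetic therapy". Once the requirement has been made, "this will be carried forward for all subsequent patients entered at the same or higher dose level". Neither section says that a repeat can happen only once.

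Section 11.3 lets a level escalate with three evaluable patients and no DLT. It stops de-escalation under one condition: "If six patients already entered at next lower dose level, the MTD has been defined".

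**The concern.** A number called an absolute maximum should hold on every path the rules allow. Here the rule that generates extra patients applies to each tabled level and carries upward only. After a repeat at Level 2, patients who later enter at Level 1 are under no carried requirement, so Level 1 can trigger its own repeat. The same holds between Level 1 and Level -1. The count of one repeated level is therefore an assumption and does not follow from the rules.

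What is at stake is the stated enrollment limit and duration that a review board would read. The planned enrollment total in section 11.4, which is 92, equals 68 plus the 24 patients that section 11.1 allows for Parts B and C, so it appears to rest on the same count.

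**Working it through.** **Inputs.** From section 11.1: cohorts of 6, 6 PK patients, 20% inevaluability, 1-2 patients per month, and the convention of 24 patients for a level that is both expanded and repeated. From section 11.2.2: expansion to 12. From section 5.3.1: the repeat and its upward-only carry-forward. From section 11.3: escalation at 0 DLTs in 3, and the stop if the next lower level already has six.

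**Formula.** Enrolled = (evaluable over the three levels + 6 PK)/(1 - 0.20), rounded up. Duration in months runs from enrolled/2 to enrolled/1.

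**The plan's own figures reproduce.**
- Base: (6 + 6 + 6 + 6)/0.8 = 30
- One level repeated: (12 + 6 + 6 + 6)/0.8 = 37.5, so 38; 19-38 months
- One level repeated, all expanded: (24 + 12 + 12 + 6)/0.8 = 67.5, so 68; 34-68 months

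**A permitted path with three repeats.**
1. Level 1 escalates with 3 patients and no DLT.
2. Level 2 reaches the vomiting or dehydration trigger and is repeated as 2A; 2A fails.
3. De-escalation goes to Level 1. It holds three patients, so the stop does not apply, and no requirement carries down.
4. Level 1 fills and reaches the trigger. It is repeated as 1A; 1A fails.
5. Level -1 opens, again with no carried requirement. It reaches the trigger and is repeated as -1A, which is tolerated.

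That is six cohorts: 36 evaluable patients at 6 each, or 72 at 12 each. A search over all paths under these rules found the same two maxima.

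**Enrollment by number of levels repeated, all three levels used.**

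| Levels repeated | Without expansion | With expansion to 12 |
|---|---|---|
| 1 (the plan) | 38 | 68 |
| 2 | (12 + 12 + 6 + 6)/0.8 = 45 | (24 + 24 + 12 + 6)/0.8 = 82.5, so 83 |
| 3 | (12 + 12 + 12 + 6)/0.8 = 52.5, so 53 | (24 + 24 + 24 + 6)/0.8 = 97.5, so 98 |

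**Durations.** 83/2 = 41.5, so 42-83 months. 98/2 = 49, so 49-98 months. 53/2 = 26.5, so 27-53 months.

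**When the stated figures are exceeded.** Two repeats at Levels 1 and 2, with Level -1 never opened, give (24 + 24 + 6)/0.8 = 67.5, again 68, and (12 + 12 + 6)/0.8 = 37.5, again 38. The excess therefore needs Level -1 as well.

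**How remote the path is.** Assume one DLT rate p at every level and count every DLT as vomiting or dehydration, which is generous.
- Level 1 must show 0/3 and then at least 2 DLTs in its next 3 patients: (1 - p)³ × [3p²(1 - p) + p³]. This is 0.053 at p = 0.20, 0.066 at p = 0.25, and at most 0.077 at any p.
- Cohorts 2, 2A, 1A and -1 must each show at least 2 of 6: probability 0.345 at p = 0.20 and 0.466 at p = 0.25.
- Product: 0.053 × 0.345⁴ is about 0.08%; 0.066 × 0.466⁴ is about 0.3%.

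**The case against.** The strongest reply is that nothing is miscalculated. Both 38 and 68 follow exactly from their stated inputs, and the text itself says that one level is counted at 12 or at 24. This stands for 38, which is called only an expected maximum and can be read as a planning assumption. For 68 it fails: disclosing an input does not make the result absolute.

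Second, the path is remote, and expansion to 12 is discretionary. Section 11.2.2 says only that it will be considered, under several conditions that include agreement of the study chair, statistician, committee leadership and IND sponsor; 98 would need it in six cohorts. The two triggers also pull against each other, since two DLTs of different classes among six patients cannot both be the vomiting or dehydration DLTs that trigger a repeat. All of this stands and limits the severity. But 68 already assumes expansion at all three levels and one level that is both expanded and repeated. Within the decision table it also needs the return to a part-filled Level 1. Counting further repeats adds no new kind of event.

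Third, a reader might take the labels -1A, 1A and 2A in section 5.3.1 as proof that all three repeats were foreseen. They are given as examples and as alternatives, and fit a single repeat at whichever level triggers it. The point rests on the carry-forward rule, not on the labels.

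Fourth, 68 is not a stopping rule. Exposure at each level is governed by the decision table in section 11.3, the weekly leadership review and the DSMC. That also stands.

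**Conclusion.** Wrong as written; minor. The rules in sections 5.3.1 and 11.3 allow Part A under Amendment #4 to exceed 68: 83 with two levels repeated and all three used, or 98 with three repeated. These are 15 and 30 patients above the stated figure. Both rest on the plan's convention of 24 per repeated level, on 6 PK patients and 20% inevaluability, and on Level -1 being opened. Without expansions the figures are 45 and 53 against 38.

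Two stronger readings are not supported. One is that 98 is the true ceiling. Section 11.2.2 counts DLTs in the PK expansion towards the MTD and allows the MTD to be exceeded at that stage, which could lead to further enrollment that neither 68 nor 98 includes. The other is that the study would expose many more children than planned or reach a wrong dose conclusion. The path has a probability well below 1% under the assumptions shown, and the determination of the MTD does not use 68.

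**What to change.** In section 11.1, stop calling 68 absolute. State that 38 and 68, with their durations of 19-38 and 34-68 months, assume that at most one dose level is repeated with required antiemetics. Give 53 and 98 (27-53 and 49-98 months) as the figures if all three levels are repeated, and note that further enrollment after DLTs in the PK expansion is not counted.

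If 68 is replaced rather than relabelled, update the planned enrollment table in section 11.4: its total of 92 = 68 + 24 would become 98 + 24 = 122.

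If the sponsor intends that only one level can ever be repeated, sections 5.3.1 and 11.1 must be reconciled so that the rules and the count agree.

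The cost is wording and a few figures. No patients are added and no analysis changes.

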5.3.3 Part C: Surgical HGG Expansion Cohort

Patients with HGG requiring resection (Part C) will be treated at the recommended phase 2 dose (RP2D) determined from the phase 1 component (Part A) of this trial for 2 doses prior to undergoing scheduled resection of their tumors (*i.e.* Surgical resection should occur after dose on Day 8 but before dose on Day 15 of Cycle 1). After recovery from surgery with wound healed (minimum 3 weeks) and meeting criteria in [Section 5.2](#), patients can resume selinexor at the same dose and schedule and continue therapy to complete Cycle 1 and continue with Cycle 2. Patients who fail to recover from surgery within 6 weeks will be removed from protocol therapy.

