#### 5.5 Definition of Dose-Limiting Toxicity (DLT)

DLT will be defined as any of the following events that are possibly, probably or definitely attributable to selinexor. The DLT observation period for the purposes of dose-escalation will be the first cycle of therapy.

Dose limiting hematological and non-hematological toxicities are defined differently.

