## 11.2 Definitions

### 11.2.1 Evaluable For Adverse Events

For all parts of the study, any patient who receives at least one dose of the study drug(s) and who experiences a dose-limiting toxicity is considered evaluable for Adverse Events. In addition, for the dose-escalation portion (Part A), during Cycle 1, patients must have the appropriate toxicity monitoring studies performed to be considered evaluable for dose limiting toxicity. In Part A, patients who do not have DLT and do not receive at least 5 out of 6 of the prescribed doses (~85%) within the first cycle for reasons other than toxicities (e.g. progressive disease) will not be considered evaluable for toxicity and will be replaced.

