### 11.2.2 Maximum Tolerated Dose

- The MTD will be the maximum dose at which fewer than one-third of patients experience DLT (See [Section 5.5](#)) during Cycle 1 of therapy.
- In the unlikely event that two DLTs observed out of 6 evaluable patients are different classes of Adverse Effects (e.g. hepatotoxicity and myelosuppression) AND all of the following conditions are met, expansion of the cohort to 12 patients will be considered:
  - One of the DLTs does not appear to be dose-related
  - The Adverse Effects are readily reversible
  - The study chair, DVL statistician, DVL committee chair or vice chair, and IND sponsor all agree that expansion of the cohort is acceptable

THIS PROTOCOL IS FOR RESEARCH PURPOSES ONLY, SEE PAGE 1 FOR USAGE POLICY

If fewer than 1/3 of patients in the expanded cohort experience dose-limiting toxicities, the dose escalation can proceed.

- The DLTs observed in the pharmacokinetic (PK) expansion cohort will be counted towards the total number of DLTs observed at the MTD during the dose escalation portion of the study. If  $\geq 1/3$  of the cohort of patients at the MTD (the dose escalation plus the PK expansion) experience DLT then the MTD will be exceeded.

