## 11.3 **Dose Escalation and Determination of MTD**

The rolling six phase 1 trial design will be used for the conduct of this study. Two to six patients can be concurrently enrolled onto a dose level, dependent upon (1) the number of patients enrolled at the current dose level, (2) the number of patients who have experienced DLT at the current dose level, and (3) the number of patients entered but with tolerability data pending at the current dose level. Accrual is suspended when a cohort of six has enrolled or when the study endpoints have been met.

Dose level assignment is based on the number of participants currently enrolled in the cohort, the number of DLTs observed, and the number of participants at risk for developing a DLT (i.e., participants enrolled but who are not yet assessable for toxicity). For example, when three participants are enrolled onto a dose cohort, if toxicity data is available for all three when the fourth participant entered and there are no DLTs, the dose is escalated and the fourth participant is enrolled to the subsequent dose level. If data is not yet available for one or more of the first three participants and no DLT has been observed, or if one DLT has been observed, the new participant is entered at the same dose level. Lastly, if two or more DLTs have been observed, the dose level is de-escalated. This process is repeated for participants five and six. In place of suspending accrual after every three participants, accrual is only suspended when a cohort of six is filled. When participants are inevaluable for toxicity, they are replaced with the next available participant if escalation or de-escalation rules have not been fulfilled at the time the next available participant is enrolled onto the study.

THIS PROTOCOL IS FOR RESEARCH PURPOSES ONLY, SEE PAGE 1 FOR USAGE POLICY

The following table provides the decision rules for enrolling a patient at (i) the current dose level (ii) at an escalated dose level, (iii) at a de-escalated dose level, or whether the study is suspended to accrual:

# Pts Enrolled	# Pts with DLT	# Pts without DLT	# Pts with Data Pending	Decision
2	0 or 1	0, 1 or 2	0, 1 or 2	Same dose level
2	2	0	0	De-escalate*
3	0	0, 1 or 2	1, 2 or 3	Same dose level
3	1	0, 1 or 2	0, 1 or 2	Same dose level
3	0	3	0	Escalate**
3	≥ 2	0 or 1	0 or 1	De-escalate*
4	0	0, 1, 2 or 3	1, 2, 3 or 4	Same dose level
4	1	0, 1, 2 or 3	0, 1, 2 or 3	Same dose level
4	0	4	0	Escalate**

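### The closure rule for Parts B and C conflicts with the Part A rules at the same dose, and its DLT window and denominator are not fixed for those parts

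*Combined protocol and SAP*

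**What the plan says.** Parts B and C are treated at the dose that Part A selects (5.3.2, 5.3.3 and 11.1). For each of them, 11.1 closes accrual "If at any time greater than one out of three patients (or 33%) of the cohort of patients experience DLT". It gives no minimum number of patients and no table of counts.

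Part A judges the same dose by other rules:

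- Section 11.3 continues after a single early DLT: "or if one DLT has been observed, the new participant is entered at the same dose level". Its decision table likewise stays at the dose level with 1 DLT in 2 or in 3 patients.
- "If two or more of a cohort of up to six patients experience DLT at a given dose level", 11.3 declares the MTD exceeded. Section 11.2.2 allows a conditional expansion to 12 as an exception.
- Section 11.2.2 defines the MTD by fewer than one-third with DLT. It adds that if at least 1/3 "of the cohort of patients at the MTD (the dose escalation plus the PK expansion) experience DLT then the MTD will be exceeded".

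On the inputs, 5.5 says: "The DLT observation period for the purposes of dose-escalation will be the first cycle of therapy". Section 11.2.1 counts a patient with a DLT as evaluable in every part. Its exclusion and replacement of DLT-free patients is limited: "In Part A, patients who do not have DLT and do not receive at least 5 out of 6 of the prescribed doses" within Cycle 1 for reasons other than toxicity are replaced.

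**The concern.** Two rules judge the tolerability of one dose, and they disagree in both directions. The Part B/C rule is stricter than Part A at the first patients and looser at 2 of 6. Section 11.1 lets Parts B and C open alongside the Part A PK expansion, so opposite decisions on the same dose could arise at the same time.

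What is at stake is whether an expansion cohort closes on an early DLT at an acceptable dose, or stays open at a DLT proportion that Part A has already called too high. If the count, window and denominator are settled only once a DLT has occurred, a pre-specified safety rule becomes a judgment made after seeing the data.

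**Working it through.** **Inputs.** Threshold and cohort size of 10 from 11.1; Part A rules from 11.2.2 and 11.3. The true DLT rate p is not in the documents, so 10%, 20% and 40% are assumptions.

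**Plan's own figures.** The plan gives no operating characteristic for the closure rule. The nearby response figures in 11.1 do reproduce: 1 − 0.80^10 = 89.3% and 1 − 0.95^10 = 40.1%.

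**Step 1: closing counts.** The smallest number of DLTs that closes the cohort at each number of patients n:

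| n | 1 | 2 | 3 | 4 | 5 | 6 | 7 | 8 | 9 | 10 |
|---|---|---|---|---|---|---|---|---|---|---|
| Literal: more than 1/3, from patient 1 | 1 | 1 | 2 | 2 | 2 | 3 | 3 | 3 | 4 | 4 |
| Exactly 1/3 also closes (33% at face value) | 1 | 1 | 1 | 2 | 2 | 2 | 3 | 3 | 3 | 4 |
| More than 1/3, from patient 3 | – | – | 2 | 2 | 2 | 3 | 3 | 3 | 4 | 4 |

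The first two rows differ only at n = 3, 6 and 9, because 33.3% is above 33% but not above one-third.

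**Step 2: comparison with Part A at the same dose.**

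| Data | Part A | Parts B/C, literal | Parts B/C, 33% at face value |
|---|---|---|---|
| 1 DLT in 2 | continue | close | close |
| 1 DLT in 3 (the third patient) | continue | open | close |
| 2 DLTs in 6 | MTD exceeded (exception possible) | open | close |

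Neither reading agrees with Part A in every row.

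**Step 3: closure probabilities.** Patients enter one at a time, outcomes are known in order, and each has DLT probability p. P(close) is the sum over n of the probability of first reaching the closing count at n. For the literal rule at p = 10%, the terms for n = 1, 2, 4, 5, 7, 8 and 10 are

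0.1000 + 0.0900 + 0.0081 + 0.0146 + 0.0020 + 0.0041 + 0.0006 = 0.219.

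The first two patients account for 1 − 0.9² = 19.0 of the 21.9 points. At p = 20% they account for 1 − 0.8² = 36.0 of 46.0.

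| Closure by patient 10 | p = 10% | p = 20% | p = 40% |
|---|---|---|---|
| Literal: more than 1/3, from patient 1 | 21.9% | 46.0% | 84.1% |
| More than 1/3, from patient 3 or needing 2 DLTs | 9.2% | 31.5% | 78.1% |
| Exactly 1/3 also closes | 29.7% | 56.4% | 89.6% |

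Part C enrolls up to 10 and closes when Part B has filled, so these are upper cases for Part C.

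**Step 4: how often 2 of 6 is reached with the cohort open.** Under the literal rule this needs no DLT in patients 1–2, one in patients 3–5 and one at patient 6: 3p²(1 − p)⁴. That is 3 × 0.01 × 0.6561 = 2.0% at 10% and 3 × 0.04 × 0.4096 = 4.9% at 20%. Early closure is therefore the more frequent conflict.

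**Step 5: window (illustration only).** Treatment may run to 24 cycles. Suppose an independent 10% DLT risk per cycle. Counting one, two or three cycles gives a per-patient rate of 10%, 1 − 0.9² = 19% or 1 − 0.9³ = 27.1%. Literal-rule closure is then 21.9%, 43.6% or 62.0%.

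**The case against.** The best defence is that the rule is clear enough. At any time means from the first patient, 33% is a rounded gloss on one in three, and the rule is simply more than 1/3. Part A's table chooses among escalating, staying and de-escalating, while 11.1 only closes accrual to an expansion cohort, so the two need not match. DLTs are reported within 24 hours (5.4) and reviewed weekly (14.4.2), and the DSMC also meets.

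Much of this stands. The rounding reading is the natural one, and missed events are unlikely. Part A is not a single proportion either, since it continues at 1 of 3 and stops at 2 of 6. But the clear reading is the one that conflicts with Part A: it closes at 1 of 2 and stays open at 2 of 6 at a dose chosen because fewer than one-third had DLT. Review meetings ensure that a DLT is seen; they do not say which count closes the cohort.

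Four stronger readings are tempting, and the documents do not support them:

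- That the rule plainly gives two answers at exactly 1/3. This requires a rounded gloss to override the fraction it explains.
- That closure probability is uncertain threefold. The 9.2% and 29.7% both come from non-literal readings at the lowest rate shown. The ratio is 56.4/31.5 = 1.8 at 20% and 89.6/78.1 = 1.15 at 40%.
- That eligible Part A patients enter the Part B DLT count because they "will be included in the evaluation rule". That sentence selects patients evaluable for response under 11.2.3, which refers back to the 11.1 rule for response. The response rule is meant.
- That Cycle 1 in Part C has no end. Patients who resume after surgery "continue therapy to complete Cycle 1 and continue with Cycle 2", so it does end for them. Only those who never resume are left unaddressed.

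**Conclusion.** The point holds as a conflict between stated rules. Read literally, 11.1 closes Part B or C on one DLT in the first one or two patients, where 11.3 continues, and leaves it open at 2 of 6, which 11.3 treats as exceeding the MTD unless the 11.2.2 exception is used. Under the literal rule, closure by patient 10 is 21.9% at an assumed 10% DLT rate and 46.0% at 20%. Other readings move this down to 9.2% and 31.5% or up to 29.7% and 56.4%. These figures assume independent patients, one-at-a-time entry with outcomes known in order, and true rates that the documents do not give.

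The inputs are a second, smaller gap. Cycle 1 is the natural window for Parts B and C, but 5.5 sets it only for escalation. No text says whether a DLT-free patient who leaves early stays in the Part B/C denominator, or how to count a Part C patient who does not resume after surgery. The passages should be reconciled before either cohort opens.

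**What to change.** Replace the closure sentence in 11.1, for both parts, with one table of closing DLT counts by number evaluable, reconciled with 11.2.2 and 11.3. It should show the first number of patients at which the rule applies and the decision at exactly 1/3. State whether the 11.2.2 expansion-to-12 exception applies. Give the DLT window and denominator for Parts B and C, including DLT-free early leavers and Part C patients who do not resume. The 11.2.1 sentence cannot simply be carried over, because it counts six doses and the Amendment #4 cycle has four.

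The choice of limit is the sponsor's. Purely as an illustration, at least 1/3 with at least two DLTs (closing counts 2 at n = 2–6, 3 at 7–9, 4 at 10–12) is consistent with Part A's 2-of-6 and 4-of-12 points. It closes by patient 10 with probability 12.5% at 10%, 38.8% at 20% and 83.5% at 40%.

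The change costs protocol wording only. The illustration does have a price against the literal rule. At a true 40% rate it closes about as often (83.5% against 84.1%) but later. The overall mean treated is 5.1 against 3.6, counting runs that never close as 10; among runs that close it is 4.2 against 2.4.
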